5.2. Procedure for Receiving Informed Consent

The Principal Investigator (or designated individual) must ensure that each trial participant (and/or the participant's parent/guardian if patient is under 16), is fully informed about the nature and objectives of the trial and possible risks associated with participation. The appropriate current ethics approved OTIS-S participant information sheet (PIS) should be provided for their consideration. Potential participants (or their parent/guardian for patients under 16) should only be asked to provide informed written consent to the study after they have had sufficient time to consider the trial and the opportunity to ask any further questions. Where appropriate, potential participants under 16 should also be given the opportunity to assent to the trial.

Remote consent is permitted providing the following steps are taken:

- A member of the research team should contact the potential participant (and/or the patient's parent/guardian if patient is under 16) to introduce the trial and to organise a telephone appointment with an Investigator in order for the Investigator to discuss the trial with the potential participant in detail.
- A copy of the appropriate current ethics approved PIS and Informed Consent Form (ICF) should be sent to the potential participant (and/or the patient's parent/guardian if patient is under 16) by email or post ahead of the scheduled appointment so that they have sufficient time to review the trial information. (If sending by post, two copies should be sent – one for the patient to retain and one to return to the site).
- During the telephone appointment the Investigator should complete the informed consent process remotely, discussing the study and ensuring that the potential participant (and/or the patient's parent/guardian if patient is under 16) is fully informed.
- If the potential participant (or the patient's parent/guardian if patient is under 16) agrees to consent the Investigator should ask them to initial the sections of the ICF and sign and date two copies. They should ask for one copy to be emailed/posted back to the site as soon as possible.
- The Investigator should record the date of verbal consent in the participant's clinical notes and confirm to the participant (and/or the patient's parent/guardian if patient is under 16) that this consent has been noted.

- The ICF should be received from the participant (or their parent/guardian) within a week of consent. Sites should follow up on any consent forms not received until they have been received, signed and filed.
- On receipt of the signed copy of the ICF from the participant (or the patient's parent/guardian if patient is under 16) the consenting Investigator should add their signature and date of signing and place in the patient file.
- A completed copy should be emailed/posted to the participant (or the patient's parent/guardian if patient is under 16) for their records.

No protocol-required assessments should be conducted until the OTIS-S consent form has been signed and dated by both the participant (or parent/guardian for participants under 16) and the Investigator, unless they are performed routinely as part of standard patient care.

Confirmation of the participant's consent (or parent/guardian's consent for patients under 16) and the informed consent process must be documented in the patient's medical notes. A copy of the signed consent form should be provided to the participant (or parent/guardian for patients under 16) and the original retained in the investigator site file, which must be available for verification by ICR-CTSU study staff or for regulatory inspection at any time.

Participants entering the trial, aged under 16 with parent/guardian's consent, who turn 16 years old during the trial will need to be reconsented using the appropriate participant information sheet/consent form. This new consent must be documented in the patient's medical notes. A copy of the new signed consent form should be provided to the participant and the original retained in the investigator site file, which must be available for verification by ICR-CTSU study staff or for regulatory inspection at any time.

5.3. Participation in other Clinical Trials

Patients who fulfil the eligibility criteria will be given the opportunity to participate in OTIS-S if they have previously participated in other clinical trials prior to recruitment.

Participation in other research should be discussed with the OTIS-S Trial Manager prior to co-enrolment.

6. TRIAL ENTRY

6.1. PART A

This section describes trial entry procedures during Part A. Procedures for trial entry and randomisation during part B will be confirmed in a protocol amendment prior to the commencement of Part B.

No protocol required assessments should be conducted until the OTIS-S consent form has been signed and dated by both the participant and the Investigator unless the assessments are performed routinely as part of standard patient care.

Trial enrolment will be performed by site staff who will log onto the trial database to register the participant. An eligibility checklist must be completed prior to registration.

The following information will be required at registration:

- Name of hospital, consultant and person registering participant
- Confirmation that participant (or parent/guardian if appropriate) has given written informed consent for trial participation

- Confirmation that participant is eligible for the trial by completion of the eligibility checklist
- Participant's full name, hospital number, date of birth, postcode, NHS/CHI number
- Participant postal or email address (depending on participant' choice for the provision of PRO questionnaires)

Site staff should register the participant by logging onto the trial database, selecting OTIS-S and completing the questions. The Trial ID will be issued, and the system will confirm participant entry into the trial.

As this is an electronic system, sites will have access at all times, but the OTIS-S trial team will only be available between 09.00-17:00 (UK time) Monday to Friday, excluding bank Holidays.

In Part A, all registered OTIS-S participants will undergo serum miRNA monitoring alongside standard surveillance of MRI/CT (see section 9 - STUDY INTERVENTION).

7. TRIAL ASSESSMENTS

The following sections describe trial assessment during Part A. Assessments during part B of the trial will be similar to part A, except that patients will either have the miRNA monitoring (with no routine cross-sectional imaging) or the cross-sectional imaging (no miRNA monitoring) according to random allocation. Both groups will have regular routine markers as in the part A schedule. There will be some additional patient-completed questionnaires (see section 8). Full details of Part B assessments will be confirmed in a protocol amendment prior to commencement of Part B.

7.1. Post Trial Entry Assessments

7.1.1. PART A

The following assessments should be conducted within 14 days **after** registration:

- Medical history
- Physical examination
- Routine tumour markers: AFP, β -HCG and LDH (investigations undertaken as part of standard care within 3 weeks prior to registration are acceptable)
- Radiological assessment as follows (investigations undertaken as part of standard care within 6 weeks prior to registration are acceptable). Ideally the same imaging modality should be used for surveillance throughout the trial.:
 - **For seminoma participants:** MRI/CT abdomen as per local practice.
 - **For dysgerminoma participants:** MRI and/or abdominal ultrasound.
- Collection of blood sample for miRNA analysis (See section 9 - STUDY INTERVENTION)

7.2. Surveillance Assessments

7.2.1. PART A

The following assessments should be conducted at the time points indicated. For scheduling purposes, a 2-week window either side of the actual time point is acceptable. Imaging should be performed within 2 weeks either side of the blood sample being taken for miRNA analysis.

3 months (m), 6m, 9m, 12m, 15m, 18m, 21m, 24m, 30m, 36m, 42m, 48m, 54m and 60m after registration in the trial.

- Routine tumour markers (AFP, β -HCG and LDH)
- Review/Reporting of SAEs as appropriate (see section 10)
- Collection of blood sample for miRNA analysis (except at 54m)* - described further in section 10
- **Required radiological assessments** (Ideally the same imaging modality should be used for surveillance throughout the trial.):
 - **For seminoma participants:** Cross-sectional abdominal imaging at 6m, 18m and 36m, preferably with MRI but CT can be used according to local practice.
 - **For dysgerminoma participants:** Cross-sectional abdominal+/-pelvic imaging at 6m, 18m and 36m, preferably with MRI. For participants under the age of 19, pelvic ultrasound (US) may be used at physician's discretion where MRI is not possible or where US is used routinely at site.
- **Additional imaging and assessments according to local practice:** In addition to the required radiological assessments above, the following can also be performed according to local practice:
 - cross-sectional imaging (abdominal+/-pelvic MRI or CT) can be performed at up to 4 further time points over the 5-year follow-up period
 - Physical examination
 - For seminoma, chest x-ray can be performed as per local practice
 - For dysgerminoma participants, low dose chest CT and transvaginal US can be performed as per local practice.
- Acceptability questionnaire to be completed by participant at 12m** (for participants 16 years old and over only)

*Note: miRNA samples taken at 9m, 15m, 21m and 42m will be analysed retrospectively in case of relapse only, and results will not be fed back to centres in real time.

**Note: Acceptability questionnaire (16 and over only) emailed or posted to participant's home address directly from ICR-CTSU, based on participant's preference, but site teams are asked to remind the participant about completion in order to maximise return rates.

7.3. Procedure for follow-up of positive routine tumour marker or finding on physical exam

[figure not shown]
Participants found to have raised markers (according to one or more of the criteria below) should have all tumour markers repeated within 1-4 weeks. If persistently elevated, this should be further investigated as per section 7.4.2:

- β -HCG>4 IU/L
- AFP >10 (if \leq 10 at baseline) OR increase of >25% above baseline (where >10 at baseline)
- LDH >1.2 x upper limit of normal

[figure not shown]
Any abnormal finding on physical examination should be followed up as per local practice.

7.4. Procedure for follow-up of different miRNA results

Please refer to the flowchart below describing follow-up procedures according to miRNA results. In the event of a negative result, surveillance should continue as described in section 7.2.

1. AFP, β -HCG and LDH

* For dysgerminoma patients under the age of 19 US may be used at physician's discretion.

1. This would be the routine surveillance MRI/CT if the positive miRNA result occurred at a time point when routine imaging was planned (6, 18 or 36m).

2. US results managed as per local practice.

3. 1. AFP, β -HCG and LDH

4. miRNA sample to be analysed retrospectively.

5. Confirmed on repeat within 4 weeks.

6. In cases where the miRNA remains positive and no other scans are planned within the routine surveillance schedule, MRI/CT should be repeated 6 months after the 3m follow-up scan. If the miRNA remain positive with negative imaging, please contact the trial team to discuss.

7.4.1. Procedure on receipt of an indeterminate miRNA result

If the miRNA test returns an indeterminate result, participants should be followed up after 6 weeks with the following assessments:

- Physical examination
- Routine tumour markers (AFP, β -HCG and LDH)
- Collection of blood sample for miRNA analysis

Results of the miRNA test (and other investigations) will then determine subsequent management as per the flowchart above.

7.4.2. Procedure on receipt of a positive miRNA result or routine tumour marker

If the miRNA test returns a positive result or routine markers are positive (and remain positive on repeat testing as per section 7.3), the potential relapse should be confirmed by MRI or CT (as per local practice, ideally the same imaging modality should be used throughout the trial) of the abdomen and pelvis and CT of the chest. For dysgerminoma participants under the age of 19 US may be used at physician's discretion. A repeat miRNA test should also be performed.

- If imaging is positive, procedures at disease recurrence, as described in section 7.6, should be followed.
- If the imaging is negative, further investigation should be conducted with ^{18}F Fluoro-deoxy glucose (FDG) PET-CT. Ultrasound of contralateral scrotal testis should also be considered in seminoma participants.
- If the FDG PET-CT is negative, participants should be assessed 6 weeks after that scan with the following assessment:
 - Routine tumour markers (AFP, β -HCG and LDH)
 - Collection of blood sample for miRNA analysis (to be analysed retrospectively)
 - For seminoma patients, ultrasound of contralateral scrotal testis if not performed at time of PET-CT.
- If the routine tumour markers are elevated, this should be confirmed as described in section 7.3, and then imaging should be repeated (MRI or CT of the abdomen and pelvis and CT of the chest, Ideally the same imaging modality should be used for surveillance throughout the trial).
- If the routine tumour markers are not elevated, participants should be assessed again after a further 6 weeks (i.e. 12 weeks after PET-CT) with the following assessments:
 - Physical examination
 - Routine tumour markers (AFP, β -HCG and LDH)
 - Collection of blood sample for miRNA analysis
 - Imaging (chest CT and with either MRI or CT abdomen and pelvis as per local practice, consider including sanctuary sites such as brain). For dysgerminoma participants under the age of 19, US may be used at physician's discretion.

In the event that the miRNA result returns to normal during repeat testing as part of the above process, please contact the trial team to discuss ongoing management on a case-by-case basis.

In the event that miRNA remains positive, but relapse has not been confirmed on imaging as part of the above process, this should also be discussed with the trial team to determine appropriate management on a case-by-case basis. Where no more surveillance imaging is scheduled (i.e. >36 months post-randomisation),

it may be appropriate to schedule a further imaging investigation 6 months after previous scan (i.e. approximately 9m after the first positive miRNA result).

Please note that the investigations detailed above are the minimum requirements for trial purposes; other investigations can be carried out on a case-by-case basis as deemed appropriate by the local investigator.

7.5. Procedure for follow-up of positive or equivocal findings on surveillance imaging

In the case of relapse detection on surveillance imaging, procedures for disease recurrence should be followed as below (section 7.6) regardless of miRNA results. In the event that a recent miRNA test has not been performed (i.e. within +/- 2 weeks of imaging), a sample should be collected for this purpose as soon as possible.

In the case of an equivocal result on imaging, imaging should be repeated at 3 months or as per local practice.

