Numerous subsequent studies have utilised the Cambridge team's pre-amplified qRT-PCR methodology to show that miR-371a-3p are highly sensitive and specific for malignant seminoma diagnosis, disease-monitoring, and detection of recurrence. One investigation of 874 patients showed serum miR-371a-3p levels at primary diagnosis provided an area under the curve (AUC) of 0.97, with a specificity of 94% at a sensitivity of 90%, and a positive predictive value of 0.97²⁸. In patients with clinical stage I disease, miR-371a-3p levels fell rapidly to normal within 24 hours following orchietomy, indicating a much shorter half-life than AFP and HCG²⁸. In patients with metastases, miR-371a-3p levels fell significantly between the first and subsequent courses of chemotherapy²⁸. Further, a retrospective pooled analysis of four independent studies in which all four candidate circulating miRNAs (miR-371a-3p, miR-372-3p, miR-373-3p, and miR-367-3p) were assessed, demonstrated that no combination of markers provided additional diagnostic benefit to miR-371a-3p alone²⁹. It was concluded that quantifying circulating miR-371a-3p alone is sufficient for malignant testicular GCT diagnosis, and, importantly, more cost-effective and easier to interpret than a larger marker panel, facilitating incorporation into routine clinical practice²⁹.

A small pilot study has shown that, in the follow-up of patients with stage I testicular GCTs³⁰, all 10 patients who had a recurrence exhibited increased miR-371a-3p levels. Levels remained non-elevated in all but one of 23 patients without recurrence³⁰. The authors concluded that miR-371a-3p detects recurrence reliably and usually several months earlier than standard investigations (markers and imaging)³⁰. Together, these data show that circulating miR-371a-3p levels accurately reflect malignant GCT burden and response to treatment. Consequently, the miR-371a-3p assay has the potential to replace scans in follow-up with estimated cost-savings of up to \$69M per year in the US¹⁸. Similar gains are expected in the UK.

Refining the circulating miR-371a-3p assay to allow clinical adoption.

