7.6. Procedure at Disease recurrence

On confirmation of disease recurrence by imaging, participants should receive relapse treatment/management as per standard of care.

At the time of disease recurrence, participants will discontinue protocol surveillance but follow-up data collection documenting relapse details, relapse treatment, any subsequent relapse/progression, and survival should continue unless the participant has explicitly withdrawn consent for this. Follow-up should be approximately 6-monthly, but can be timed to align with routine care visits.

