11.2. Endpoint Definitions

11.2.1. Part A Primary Endpoint

The primary endpoint for Part A is sensitivity of miRNA for relapse detection, defined as the number of relapses detectable on miRNA testing before or at the same time as detection on imaging (or via other components of standard surveillance) as a proportion of the total number of relapses identified via standard investigations. In all cases, date of detection will be taken to be the date of the sample collection or imaging/investigation (rather than the date the results were available) and a 2-week window will be allowed from detection on imaging/standard investigations to allow for scheduling of miRNA testing sometimes occurring after imaging. Detection on miRNA requires a positive result according to lab-specific normal ranges, and the date of sample collection will be taken to be the date of relapse detection.

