11.3.2. Part A Analysis Sets

All Part A participants will be included in the analysis; however, analyses of specific endpoints will be dependent on availability of data. In particular, the estimation of sensitivity will include all patients with a confirmed relapse on imaging and a miRNA test performed within 2 weeks of detection on imaging. Seminoma and dysgerminoma patients will be analysed together, but tumour type-specific estimates for sensitivity, specificity and lead time will also be reported and considered when interpreting results. However, the dysgerminoma cohort is expected to be very small and this analysis will be considered exploratory.

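### The Part A recurrence miRNA sample is timed only against imaging, so a sample drawn after relapse treatment has started could be scored as a missed relapse

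*Protocol*

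**What the plan says.** **Collection.** Protocol section 7.5 deals with relapse seen on surveillance imaging. Where no miRNA test lies within 2 weeks either side of the scan, "a sample should be collected for this purpose as soon as possible". Footnote 5 to the schedule in 7.8.1 likewise asks for a sample if there is none within 2 weeks of the confirmatory imaging. Footnote 4 says this sample is analysed retrospectively and its result is not returned to centres in real time.

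**Scoring.** In section 11.2.1, "a 2-week window will be allowed from detection on imaging/standard investigations to allow for scheduling of miRNA testing sometimes occurring after imaging". It adds: "Detection on miRNA requires a positive result according to lab-specific normal ranges". Detection before imaging also counts. Section 11.3.2 restricts the sensitivity estimate to "all patients with a confirmed relapse on imaging and a miRNA test performed within 2 weeks of detection on imaging".

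**Treatment.** Section 7.6 says: "On confirmation of disease recurrence by imaging, participants should receive relapse treatment/management as per standard of care". It does not link the start of treatment to the miRNA draw.

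**Marker behaviour.** Section 1.1.3 reports that in clinical stage I disease "miR-371a-3p levels fell rapidly to normal within 24 hours following orchietomy", and that in metastatic disease levels fell significantly between the first and later chemotherapy courses.

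**The concern.** The sample that decides whether a relapse was detected is defined by its distance from the scan, while treatment may start as soon as the scan confirms relapse. The window for a valid sample can therefore extend past the start of treatment. A sample drawn in that overlap measures the treated state. If it is negative, or indeterminate after partial clearance, it does not meet the requirement for a positive result, and the relapse becomes a miss for a reason unrelated to the assay's sensitivity.

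The error acts in one direction: it understates sensitivity and favours a wrong decision not to proceed. The Part A rule in sections 11.1.1 and 11.3.1 allows only one miss in 11. Under section 11.4, more than one miss before 11 relapses prompts the oversight committees to consider the value of continued recruitment. Because centres do not receive the recurrence result in real time, they have no clinical reason of their own to draw the sample before treatment. That prompt has to come from the protocol.

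**Working it through.** **1. The stated design reproduces.** Inputs from section 11.1.1: threshold 75%, expected sensitivity 95%, 11 relapses, proceed if at least 10 are detected, one-sided alpha 0.2, power 80%. Exact binomial:

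- Alpha = P(X ≥ 10 | 11, 0.75) = 11 × 0.75^10 × 0.25 + 0.75^11 = 0.155 + 0.042 = 0.197.
- Power = P(X ≥ 10 | 11, 0.95) = 11 × 0.95^10 × 0.05 + 0.95^11 = 0.329 + 0.569 = 0.898.

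This is the smallest exact design that meets both limits. The later rules also meet theirs: 19/21 against 80% gives alpha 0.179 and power 0.915; 26/28 against 85% gives alpha 0.187 and power 0.837. The design figures are not in question.

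**2. Effect of one artefactual miss at 95% true sensitivity.** One relapse is fixed as a miss and the rest are left to chance.

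| Rule | No artefact | One forced miss |
|---|---|---|
| 10/11 | 0.898 | 0.95^10 = 0.599 |
| 19/21 | 0.915 | P(X ≥ 19 of 20) = 0.736 |
| 26/28 | 0.837 | P(X ≥ 26 of 27) = 0.606 |

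Two forced misses make 10/11 impossible.

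**3. Effect of an assumed share.** Let f be the share of otherwise detectable relapses scored negative only because the sample followed the start of treatment. The protocol gives no value; 2% to 10% is an assumption chosen to show the range. Effective sensitivity is 0.95 × (1 − f).

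| f (assumed) | Effective sensitivity | 10/11 | 19/21 | 26/28 |
|---|---|---|---|---|
| 0 | 0.950 | 0.898 | 0.915 | 0.837 |
| 2% | 0.931 | 0.827 | 0.827 | 0.696 |
| 5% | 0.9025 | 0.708 | 0.663 | 0.477 |
| 10% | 0.855 | 0.511 | 0.395 | 0.207 |

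**4. Where the exposure lies.** Section 7.2.1 pairs each required scan (6, 18 and 36 months) with a miRNA sample within 2 weeks. Section 7.4.2 asks for a repeat miRNA test when persistently raised routine markers lead to confirmatory imaging. Both routes normally supply a sample close to the scan. What remains is off-schedule or local-practice scans, missed samples, and paired samples drawn after the scan, which 7.2.1 permits and 11.2.1 anticipates.

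**5. What a false miss requires.** All of the following must hold: no earlier positive sample; no pre-treatment sample in the window; treatment started within 2 weeks of imaging; a sample drawn after that start but still within 2 weeks; and a marker level no longer positive. A sample later than 2 weeks takes the relapse out of the 11.3.2 set and is not scored as a miss.

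**The case against.** The strongest reply is that this is a wording gap that will seldom matter. The five conditions above must coincide, and an instruction to draw the sample promptly already favours a draw before treatment. The biology is also less direct than it looks. The 24-hour figure concerns removal of the primary in stage I disease, not excision of a relapse. The chemotherapy finding is a fall between courses, not loss of positivity within days of a first dose. Relapse treatment data are already collected under 7.6, the IDMC reviews relapses as they occur, and the laboratory manual or SAP, which are not shown, may address the point.

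Most of this stands, and it limits the frequency. It does not close the gap. A SAP can set aside a post-treatment sample, but it cannot recover a pre-treatment sample that was never drawn, so the collection instruction belongs in the protocol.

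A reader might infer more than the text supports in two ways:

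- **That marker-detected relapses are exposed in the same way.** They are not, because 7.4.2 already asks for a repeat miRNA test alongside confirmatory imaging.
- **That a false miss is likely.** If 2%, 5% or 10% of relapses had only a post-treatment sample, the chance of at least one among 11 would be 1 − (1 − q)^11 = 20%, 43% or 69%. Those are chances that such a sample exists, under an assumed share. They are not chances of a false miss, since an earlier positive still counts as detection and a treated sample may still be positive.

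**Conclusion.** The point holds in a limited form. As written, the sampling and scoring rules allow a relapse to be scored as missed on a sample taken after its treatment began, and nothing in the protocol says such a sample should be handled differently. The bias would be towards understated sensitivity. One such event among the first 11 relapses lowers the chance of meeting 10/11 from 0.90 to 0.60, assuming 95% true sensitivity and independent relapses.

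How often it would occur cannot be derived from the document, which gives no interval from scan to treatment; it is probably low. The figures by share f illustrate an assumed range and are not an estimate. The case for acting rests on a large effect per event, a rule with room for one miss, and a remedy that costs almost nothing.

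**What to change.** **Collection (7.5 and 7.8.1 footnote 5).** State that the recurrence sample is to be drawn before relapse treatment or excision starts, without delaying care. Record the treatment start date beside the sample date on the eCRF.

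**Scoring (11.2.1 and 11.3.2).** State that:

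- a sample drawn after that start counts neither as detection nor as a miss, whatever its result;
- a relapse with no pre-treatment sample in the window is not evaluable and does not count towards the 11, 21 or 28 relapses;
- for an evaluable relapse, any positive pre-treatment sample up to the end of the window counts as detection, as 11.2.1 already provides for earlier positives;
- a sensitivity analysis includes the non-evaluable relapses.

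The rule must not depend on the result. Dropping only post-treatment negatives while keeping post-treatment positives would bias sensitivity upward and make a false decision to proceed easier. Judging detection on the last pre-treatment sample alone would conflict with 11.2.1, where any earlier positive qualifies.

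**Cost.** A sentence or two in each section and one date check; no extra blood draw and no change to when treatment starts. An occasional relapse becomes non-evaluable, which slightly delays reaching 11. Section 11.3.2 already leaves out relapses without an in-window test, so this extends an existing rule. With 11, 21 and 28 counted on evaluable relapses, the binomial rules keep their design properties (0.197 and 0.898 for 10/11).
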